11.4 Study Records Retention

Study records will be retained for at least seven years after completion of the study.

12 Statistical Plan

12.1 Study Hypotheses and Planned Analyses

Calibration Phase I

The objective of the Phase 1 of this study is to use data obtained from subjects who have consumed alcohol in a controlled laboratory setting to develop a model of the relationship between BrAc and TAC measurements that will allow for the determination of estimated blood alcohol levels (BAL) from TAC data collected over extended periods of time.

The results of several studies support the expectation that for most subjects the time to reach peaked alcohol concentrations (Tmax) will be greater for TAC as compared BrAc values [20-21]. In contrast, maximal BrAc concentration (Cmax) values are expected to be smaller be for TAC values collected during test session as compared to those obtained for BrAC measurements. Nevertheless, if TAC values detected by the test device are directly related to blood alcohol levels there should be a strong correlation between the CMax for both TAC and BrAc measurements. Therefore, we hypothesize that for correlations between Cmax values for TAC and BrAc values should be have an r value of 0.8 or greater. A finding consistent with this hypothesis will provide evidence that the test alcohol monitor is able to detect TAC levels that are directly related to BAL.

Validation Phase

Validation Phase

TAC data collected during validation phase will be converted into predicted BAL values for individual subjects using the models developed in the Phase 1 of this investigation. Data obtained during the validation phase will be inspected to determine if there are differences in the sensitivity between the breathalyzer and the wristwatch sensor. Time concentration curves for BrAc and predicted BAL values will be produced for each subject. These curves will be examined to check whether there are any systematic differences between these two measures in the time needed to reach maximal concentration levels for each of the subjects (Tmax) and between the values obtained at the maximum concentration levels (Cmax).

Predicted BAL that will be determined from TAC data are expected to be equivalent to BrAc concentrations. We, therefore hypothesize that there will be a strong correlation between BAL and BrAc measurements obtained at the same time points for the individual subjects. The reference breathalyzer response is known to be linear over the range of expected blood alcohol levels in the study [23]. Therefore, the breathalyzer and predicted BAL values are expected to be linearly related to each other. To confirm the hypothesis that these values are highly linearly related an analysis will be conducted in which repeated measures correlation coefficient (rcmm) between BrAc and BAL will be obtained. In contrast to a simple correlation analysis of data in which repeated measures collected from individual subjects are used, here will be no violation of the assumption of independence of observations when rcmm values are utilized as the measure of the extent of correlation between these values [Bakdash and Marrusich, 2017].

Calibration Study of a Wearable Noninvasive Blood Alcohol Monitor
Final V1.8 4.24.19

Data obtained in the validation phase of this study will be analyzed using the proc glm procedure for SAS 9.4. This data will include values for individual subjects obtained for each time-point at which BrAc measurement were made and corresponding predicted BAL values determined for these subjects. This data will be analyzed using following general linear model:

BAL= BrAc sub

This model is equivalent to an analysis of covariance model in which subjects (sub) are a covariate. This model will allow for the determination of whether BrAc and BAL values are significantly related to one another. The correlation coefficient [rcmm] for relationship between BAL and BrAc will be determined using the following equation first mentioned by Bland and Altman [24] with sum of squares values being obtained from the results of our glm analysis: $rcmm = \text{square root} [\text{Sum of Squares BAL} / (\text{Sum of Squares BAL} + \text{Sum of Squares Residual})]$

Since both BrAc and BAL measurements are hypothesized to be linear, the rcmm value is expected to be >0.80 with high correlation power. The statistical null hypothesis is that the predicted BAL measurements are not related to the standard breathalyzer measurements. The study is designed to maintain a probability of Type I and Type II error rates with respect to the null hypothesis at $p<0.05$.

Given that BAL and BrAc are expected to be equivalent it is also hypothesized that there will be a strong correlation between Cmax and Tmax values. Pearson correlation coefficients for correlation analysis between both Cmax and Tmax determined from individual subjects' BrAc and BAL curves, therefore, are expected to be 0.8 or greater, with p values being less than 0.05.

Hypothesis	Planned Analyses
1. There will be a significant correlation between BrAc predicted BAL measures	Repeated measures correlation analysis of wristwatch TAC measurements and contemporaneous BAC measurements from breathalyzer.
2. There will be a significant correlation between Cmax and Tmax values obtained for paired BrAc and predicted BAL measurements.	Pearson correlation analysis for Tmax and Cmax values obtained for BrAc and predicted BAL data.

We expect that the results of this study will demonstrate the effectiveness of the developmental wristwatch transdermal alcohol sensor. Furthermore, these results and the developmental work to calibrate this wristwatch will contribute significant knowledge toward the understanding of reliable measurement of blood alcohol via transdermal routes.

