Calibration Phase I. The calibration phase of this study is designed to gather data to assist in developing an equation to account for the lag in TAC readings and transform these readings into an approximation of alcohol breath readings. In this calibration phase subjects will be given a measured dose of alcohol to achieve a peak BAL level of 0.05 g/dL after a one hour drinking session. The volume of alcohol will be calculated using an online tool developed by UW-Madison (<http://dionysus.psych.wisc.edu/WebCMS/baccalc.htm>) based on a formula described by Watson [14]. The hour-long drinking session will be followed by a five hour observation period to ensure that subject reach peak TAC. Blood alcohol level will be measured simultaneously using the transdermal sensors and the breathalyzer for the duration of the drinking period and observation period. Breathalyzer readings will be taken every 15 minutes during the entire experiment and transdermal sensors will log data continuously. To ensure residual alcohol in subjects' mouths does not provide a false breath alcohol reading, subjects will rinse their mouth twice with water after consuming a saltine cracker prior to each breathalyzer given while the subject is consuming alcohol. Subjects will remain in the drinking lab for up to five hours to allow for measurement of the peak transdermal alcohol concentration. Given the length of observation, we estimate that subjects will fully metabolize the alcohol they received during the calibration session and they will have a BAL of 0.00 g/dL when the calibration session is over. In the event that a drinking session is halted or the subject has a very slow rate of metabolism, we require that subjects remain in the laboratory until their BAL, as measured by breathalyzer, reaches 0.04 g/dL or less. The drinking session will be video-recorded to provide a record of the exact timing of breathalyzer readings. If methodology or safety issues are uncovered during the Phase I of this study, the protocol may be amended to address these issues prior to completing Phase II.

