If a subject completes Phase I and is unable to complete Phase II for any reason, replacement subjects will be recruited to complete Phase I and II consecutively. It is estimated that 36 subjects will be consented to yield 12 subjects that will complete Phase I and 9 subjects that will complete Phase II. Based on past experience with subject attrition, it is estimated that 33% of the Phase I subjects will be replaced at the time of phase II. Given the sample size requirements for this study are 9 subjects to complete both trials, the total sample size is estimated to be 12 subjects taking into account the possibility that three subjects will be lost to follow-up between trials one and two. If subjects are lost, when these subjects are replaced they will complete both the calibration session and validation session over the period of approximately 60 days.

Subject compensation

Subjects will be compensated up to \$340 for completion of all study activities. In addition to reimbursements for each study visit, subjects who complete all study visits will receive a completion bonus at the end of the study. If at any time subjects are discontinued from the study during a visit, subjects will be paid a portion of the payment based on time completed (e.g., 1

Calibration Study of a Wearable Noninvasive Blood Alcohol Monitor

Final V1.8 4.24.19

hour completed of two-hour visit = 1/2 of payment). Note there is an exclusion for payment due to UDS+ at the baseline.

Subjects will receive the following reimbursements:

Baseline assessment	\$40
Phase I BAL Calibration session	\$100
Phase II eligibility determination session	\$40
Phase II BAL validation session	\$100
Completion Bonus	\$60

10 Assessment of Safety and Data Safety Monitoring Plan (DSMP)

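### The Cmax and Tmax correlation targets of 0.8 are inconclusive when missed, and when met show association rather than the equivalence the plan expects

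*Combined protocol and SAP*

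**What the plan says.** Section 12.1 sets a numerical expectation for Phase I: "we hypothesize that for correlations between Cmax values for TAC and BrAc values should be have an r value of 0.8 or greater". A finding in line with it "will provide evidence that the test alcohol monitor is able to detect TAC levels that are directly related to BAL". The Phase I paragraph attaches no null value, confidence interval, p value or power.

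For Phase II, section 12.1 expects the converted sensor readings (predicted BAL) to be equivalent to BrAC. It then gives Pearson correlations for Cmax and Tmax, which "are expected to be 0.8 or greater, with p values being less than 0.05". It also says each subject's two curves will be examined for systematic differences in Tmax and Cmax, but names no statistic for this.

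On numbers, section 9 estimates that "36 subjects will be consented to yield 12 subjects that will complete Phase I and 9 subjects that will complete Phase II". On dosing, section 5 says subjects will be "given a measured dose of alcohol to achieve a peak BAL level of 0.05 g/dL after a one hour drinking session", with the volume calculated "based on a formula described by Watson". The Phase II session has the same target.

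The primary outcome (section 4.2.1) is the Phase II repeated measures correlation, which is a within-subject measure. Section 12.2 makes Pearson correlations of AUC and Cmax the fallback if a time lag spoils that analysis, and quotes a power of 0.82 for r = 0.8 with 9 subjects.

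**The concern.** Three features combine.

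- The target is a point value for a correlation estimated from 12 or 9 pairs, so sampling error alone moves the result well to either side of 0.8.
- A correlation across subjects depends on how far the subjects' true peaks differ as well as on how well the sensor reads them. The design aims everyone at the same peak, so a good sensor could give a modest r simply because there is little spread to track.
- The Phase II text expects equivalence, but Pearson r cannot see a constant offset or a scale error.

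Two misreadings are at stake: taking r below 0.8 as failure of the device, and taking r of 0.8 or more as proof that the watch reads the same as the breathalyzer.

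**Working it through.** **Inputs from the documents.** Threshold 0.8 (12.1); n = 12 for Phase I and n = 9 for Phase II (section 9); common target peak 0.05 g/dL (section 5); stated power 0.82 at r = 0.8, n = 9 (12.2). The documents give no SD of Cmax or Tmax for either device, and 12.2 says the sensor's sensitivity in humans is unknown.

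**1. The plan's own figure.** For a two-sided test of zero correlation at 0.05, the critical value is r = t/√(n − 2 + t²). With n = 9, t = 2.365 on 7 df, so r = 2.365/√(7 + 5.59) = 0.666. Simulating the sampling distribution of r under bivariate normality at a true r of 0.8 gives power 0.820, which matches the plan. This is power to reject zero, not the chance of observing 0.8 or more. For n = 12 the same test has critical r 0.576 and power 0.93.

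**2. Chance of observing r ≥ 0.8** (same sampling distribution):

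| True r | n = 12 | n = 9 |
|---|---|---|
| 0 | 0.001 | 0.005 |
| 0.5 | 0.056 | 0.10 |
| 0.7 | 0.27 | 0.32 |
| 0.8 | 0.55 | 0.56 |
| 0.9 | 0.90 | 0.87 |

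At a true r of 0.8 the miss rate is 1 − 0.55 = 0.45 (n = 12) or 1 − 0.56 = 0.44 (n = 9). The p < 0.05 condition in Phase II adds nothing to the 0.8 threshold, because at n = 9 any r above 0.666 already meets it.

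**3. Interval at an observed 0.8** (Fisher z, atanh 0.8 = 1.099):
- n = 12: 1.099 ± 1.96/√9 = 1.099 ± 0.653, back-transformed to 0.42 to 0.94.
- n = 9: 1.099 ± 1.96/√6 = 1.099 ± 0.800, back-transformed to 0.29 to 0.96.

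**4. Effect of the common target peak.** If the sensor reads the true peak plus independent error of SD e, and peaks have SD s across subjects, expected r = s/√(s² + e²). Both SDs are assumptions. With e = 0.005 g/dL:
- s = 0.003: 3/√(9 + 25) = 0.51; P(r ≥ 0.8) at n = 12 about 0.06
- s = 0.005: 5/√(25 + 25) = 0.71; about 0.29
- s = 0.010: 10/√(100 + 25) = 0.89; about 0.89

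The sensor error is identical in all three rows. BrAC Tmax is also read only every 15 minutes after a fixed drinking hour. That limits its spread too, but the documents give nothing from which to size this.

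**5. What r cannot see.** For any constant a and positive b, corr(a + bX, Y) = corr(X, Y). A watch reading 20% high throughout would show 0.06 for a true 0.05 g/dL, with r unchanged. Bias is a practical possibility: section 9 says Phase II uses second generation sensors while the conversion model comes from Phase I.

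**6. Would a within-subject ratio do instead?** Take s = 0.003 and e = 0.005 around 0.05. A useless device that always reads 0.05 has a sensor/BrAC Cmax ratio CV of 6.1%; the real sensor has 10.1%. The limits of agreement behave alike: ±1.96 × 0.003 = ±0.006 for the constant, ±1.96 × 0.005 = ±0.010 for the sensor. With narrow peaks, neither summary shows whether the device tracks differences between people. Correlation is the summary that addresses tracking, so it has to stay.

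**The case against.** The strongest reply is that a reader might infer that the Phase I result cannot support the plan's conclusion whichever way it falls. The documents do not bear that out. The conclusion in 12.1 is one of association. An observed 0.8 at n = 12 gives t = 0.8√10/0.6 = 4.22, two-sided p = 0.002, and an interval that excludes zero. Such a result is rare with no relation (0.1%) or a moderate one (5.6% at a true r of 0.5). Narrow peaks make the threshold harder to reach, so they do not weaken a pass. This stands: the weakness lies in a miss, and in reading a pass as accuracy.

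A reader might also infer that the threshold decides something. It does not. It is worded as a hypothesis, no step depends on it, and Phase II starts once all subjects have finished Phase I and the model is complete. The primary correlation uses each subject's rise and fall, which a common target peak does not restrict in the same way. This stands too, although the fallback in 12.2 would give the Cmax correlation more weight if it were used.

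Third, landing above one's own true value about half the time is true of almost any estimate, and at a true r of 0.9 the pass rate is 90%. That is fair, but the plan names 0.8 itself and does not say how a miss would be read.

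Fourth, 0.05 g/dL is a target, and achieved peaks may scatter widely. That is correct, and the loss cannot be sized from the documents. Only its direction is certain.

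Finally, 12.1 already plans to look at the curves for systematic Cmax and Tmax differences. That is the right check, but it has no statistic attached.

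**Conclusion.** The point holds in limited form, for supporting hypotheses rather than for the primary outcome. A Cmax or Tmax correlation below 0.8 would not be evidence that the sensor fails: a sensor at exactly the hypothesised value misses about 45% of the time in either phase, and a narrow spread of peaks would lower r further for the same error. A correlation of 0.8 or more supports a relation between the two measures. It does not support the equivalence that 12.1 expects in Phase II, because constant and proportional bias leave r unchanged.

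The pass rates assume bivariate normality and the intervals use Fisher z. The 0.51 to 0.89 range rests on assumed SDs and illustrates direction only; the documents do not show that the spread of peaks will in fact be small.

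**What to change.** - **Phase II:** report predicted minus BrAC Cmax and Tmax as a mean difference with 95% CI and limits of agreement. Name these as the statistics for the planned check on systematic differences, and rest any statement of equivalence or accuracy on them.
- **Both phases:** keep Pearson r, with its 95% CI and the observed SD of BrAC Cmax beside it.
- **Phase I:** keep the sentence on what a consistent finding shows, limited to association. State in advance that r below 0.8 is inconclusive when the spread of peaks is narrow.
- The Phase I TAC/BrAC Cmax ratio may be reported as a description, but should not replace r, for the reason in step 6.

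The cost is some wording and a few extra summary lines, with no new data. The drawback is imprecision: with 9 completers the 95% CI for a mean difference is ±2.306 × SD/√9 = ±0.77 SD, and the limits of agreement are less precise still.

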4.2.2 Secondary Outcome Measures

In addition to the determination of correlation between BAL and transdermal alcohol concentration (TAC) as measured by a reference breathalyzer and the developmental KWJ wrist device, respectively, we anticipate that Phase I of this study (the first alcohol self administration trial) will provide a means to determine the characteristic time lag between BAL and TAC [12] and furthermore allow development of a preliminary model for correcting TAC measurements for this lag.

5 Study Design

Calibration Study of a Wearable Noninvasive Blood Alcohol Monitor

Final V1.8 4.24.19

This is a device calibration study designed for healthy non-treatment-seeking drinkers. The drinking lab portion of this study is an adaptation of an established human laboratory self-administration procedures [13]. Subjects who consent to this study will complete two alcohol self-administration sessions, one in the Calibration phase (Phase I) of the study and one in the Validation phase (Phase II) of the study.

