3) *Alcohol Administration.* After 60 minutes of Zero BAL observation the drinking self-administration session will begin. At the start of the alcohol administration session the subject will be given a pre-determined volume of alcohol designed to raise BAL to 0.05 g/dL. The volume of alcohol will be calculated using an online tool developed by UW-Madison (<http://dionysus.psych.wisc.edu/WebCMS/baccalc.htm>) based on a formula described by Watson⁵⁹. The hour-long drinking session will be followed by a five hour observation period to ensure that subject reach peak TAC. Blood alcohol level will be measured simultaneously using the transdermal sensors and the breathalyzer for the duration of the drinking period and observation period. Breathalyzer readings will be taken every 15 minutes during the entire experiment and transdermal sensors will log data continuously. To ensure residual alcohol in subjects' mouths does not provide a false breath alcohol reading, subjects will rinse their mouth twice with water after consuming a saltine cracker prior to each breathalyzer given while the subject is consuming alcohol. Subjects will have access to streaming entertainment during this period, but will be asked to not use personal electronics for the duration of the self-administration session. This drinking session will be video recorded to confirm exact times of BAL readings taken with the breathalyzer. Subjects will remain in the laboratory until their BAL, as measured by breathalyzer, reaches 0.04 g/dL or less.

4. *Observation.* Subjects will remain in the drinking lab for five hours of observation following alcohol administration. Breathalyzer readings will be taken every 15 minutes during the observation and transdermal sensors will log data continuously. Data from this observation will be used to develop a model that adjusts for the lag in peak TAC relative to measured BAL using a breathalyzer. Subjects will continue to have access to streaming entertainment and will also

Calibration Study of a Wearable Noninvasive Blood Alcohol Monitor

Final V1.8 4.24.19

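### Peak time is the only timing measure the plan names; with 15-minute breath readings it is too imprecise in a single subject to show residual lag, so 12.1 should add a whole-curve shift estimate

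*Combined protocol and SAP*

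**What the plan says.** - **Secondary outcome (4.2.2).** Phase I "will provide a means to determine the characteristic time lag between BAL and TAC" and is to "allow development of a preliminary model for correcting TAC measurements for this lag". No estimator, interval or target precision is given for the lag.
- **Phase I session (Section 9, Observation).** The data serve to "develop a model that adjusts for the lag in peak TAC relative to measured BAL using a breathalyzer". On sampling: "Breathalyzer readings will be taken every 15 minutes during the observation and transdermal sensors will log data continuously".
- **Calibration Phase (12.1).** TAC is expected to peak later than BrAC in most subjects.
- **Validation Phase (12.1).** Each subject's curves are checked for "systematic differences between these two measures in the time needed to reach maximal concentration levels for each of the subjects (Tmax"). The two measures are BrAC and predicted BAL. Predicted BAL is TAC already converted by the Phase I model, so this is a check on residual timing error, not on the raw lag.
- **Hypothesis 2 (12.1).** The only formal timing analysis is "Pearson correlation analysis for Tmax and Cmax values obtained for BrAc and predicted BAL data", with r of 0.8 or more and p below 0.05 expected.
- **Primary analysis (12.1) and fallback (12.2).** The repeated measures correlation uses same-time pairs and estimates no shift. If a lag makes it unusable, the plan turns to Pearson correlations of AUC and Cmax, which do not estimate a lag either.

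**The concern.** A peak time takes one reading from each curve, at the place where the curve changes least. With breath on a 15-minute grid, small reading errors decide which of two or three near-equal values is the highest. The rising and falling limbs, which carry most of the timing information, do not enter a Tmax difference.

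What is at stake is interpretation. If the repeated measures correlation comes out low in Phase II, the team will want to know whether the watch is noisy or whether the lag correction is off by 10 to 20 minutes. The only timing check in the plan is a poor tool for that question. The Tmax correlation in hypothesis 2 has the same weakness and could fail for a watch that works well.

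**Working it through.** **1. The plan's own figure.** Section 12.2 gives power 0.82 for a Pearson correlation (AUC, Cmax) at r = 0.8 with 9 subjects. A two-sided 5% test of r under bivariate normality, with 400,000 simulations, gives 0.820, so the figure reproduces. The plan states no comparable figure for Tmax or for the lag.

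**2. Inputs.** From the documents: 60 minutes of drinking, then 300 minutes (Phase I) or 180 minutes (Phase II) of observation; breath every 15 minutes; continuous watch log; target peak 0.05 g/dL; 12 subjects in Phase I and 9 completers. Assumed, because the documents give no values: first-order absorption, elimination 0.012 to 0.020 g/dL/h, watch gain 0.6, 1-minute watch data with autocorrelated noise and 15-minute smoothing, and noise SD 0.001 to 0.005 g/dL for each device. Section 12.2 itself says the sensor's sensitivity in humans is not known.

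**3. Grid and flat peak.** Rounding to a 15-minute grid alone gives an SD of 15/√12 = 4.3 minutes. The assumed typical breath curve stays within 0.002 g/dL of its peak for about 35 minutes, which is 35/15 = 2.3 reading intervals. Most of the Tmax error therefore comes from the flat top.

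**4. Error in one subject's lag.** Two estimators were applied to the same simulated data: (a) Tmax(watch) − Tmax(breath); (b) the shift that gives the best least-squares fit of the whole curves with free gain and offset, which is close to maximising the correlation. For a pure delay:

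| Noise SD (g/dL) | Tmax difference, error SD (min) | Alignment, error SD (min) | Ratio |
|---|---|---|---|
| 0.001 | 9–10 | 1.4–1.6 | 6–7 |
| 0.002 | 15–16 | 2.7–3.0 | 5–6 |
| 0.003 | 19–21 | 4.3–4.5 | 4–5 |
| 0.005 | 25–26 | 7.6–8.0 | 3.2–3.3 |

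Other settings: watch read only at breath times, ratio 3.9 to 7.8; delay plus smoothing, 2.5 to 6.8; sharp peak, 3.3 to 5.3; unsmoothed 1-minute watch data, 6 to 15. A second simulation of a 240-minute Phase II session, with the shift chosen by maximum correlation with the breath readings (the form proposed below), gave 11.5, 15.0 and 18.5 minutes for Tmax against 1.6, 2.9 and 4.0 for the shift. It assumed breath noise of 0.001 to 0.003 and watch noise of 0.002 to 0.004.

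**5. Mean lag.** Total SD = √(between-subject SD² + error SD²). With error SDs of 15.4 and 2.8 (noise 0.002):

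- Common lag, n = 12: SE 15.4/√12 = 4.4 against 2.8/√12 = 0.8 minutes.
- Between-subject SD 20: √(400 + 237) = 25.2 against √(400 + 8) = 20.2, a ratio of 1.25; SE 7.3 against 5.8 minutes (simulated directly: 7.0 against 5.5).

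Over between-subject SDs of 10 to 30 minutes the simulated ratio is 1.1 to 1.9.

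**6. Size of lag that matters.** For a noise-free watch, a constant residual lag of 10, 15 or 20 minutes alone gives r of about 0.95, 0.90 or 0.83 (a rerun gave 0.96, 0.91 and 0.85). At noise 0.002, a 15-minute residual lag in one subject is 15/15.4, about 1 error SD, by Tmax, and 15/2.8, about 5 error SDs, by alignment.

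**7. Tmax correlation in hypothesis 2.** With the lag removed perfectly, the simulated correlation between the two Tmax values was 0.63, 0.38 and 0.22 at noise 0.001, 0.002 and 0.003, and 0.25, 0.10 and −0.01 with a sharp peak. With 9 subjects, p < 0.05 needs r of at least 2.365/√(7 + 2.365²) = 0.67. The reason is that true peak times vary little in these curves (SD about 8 minutes, or about 1 minute with a sharp peak) compared with the reading error.

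**The case against.** The other side has four fair arguments.

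- **The Phase I estimator is open.** A reader might infer that the secondary-outcome lag is judged from Tmax, that the other readings go unused, or that a peak-based correction would shift the curves too far. The documents do not support this. Section 4.2.2 names no estimator. Section 5 speaks of an equation for the lag in TAC readings, and 12.1 of a model relating BrAC and TAC measurements. Such a model could use the whole curves. The phrase about peak TAC in Section 9 describes an aim and does not fix a method. This objection stands.
- **The usefulness rule is not exposed.** A reader might infer that poor Tmax precision threatens the r > 0.9 rule in 12.2. That rule rests on same-time pairs and already penalises residual lag, so a rough Tmax inspection cannot make a lagging watch pass. This stands. The loss is in explaining a low r.
- **A characteristic lag is a group quantity.** For the group mean the advantage is small if subjects truly differ. Section 12.1 expects a later TAC peak only in most subjects, which suggests that they do. This stands for the mean, but the Validation Phase check is made subject by subject, where the full advantage applies.
- **The two estimators can measure different things.** If the skin signal is broadened as well as delayed, neither is simply the true lag. With a 20-minute delay plus a 40-minute time constant, alignment returned about 52 to 54 minutes. This stands, and is a reason to show both.

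**Conclusion.** The concern holds in a limited form. Peak time is the only timing measure the plan names, no lag estimator is prespecified, and under every noise level tried the Tmax difference is clearly the less precise measure in a single subject: error SD about 9 to 26 minutes against 1.4 to 8, usually 3 to 7 times worse (extremes 2.5 and 15). The Validation Phase check as written therefore cannot reliably separate residual lag from sensor noise as the cause of a low repeated measures correlation. By the same reasoning, the expected Tmax correlation of 0.8 could fail with a well-corrected watch.

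The sizes rest on assumed noise, absorption and elimination. The direction did not change across flat and sharp peaks, pure delay and delay with smoothing, or continuous and 15-minute watch data. The point improves a secondary and diagnostic analysis; it does not put the primary analysis in doubt.

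**What to change.** In 12.1:

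- For each subject and session, estimate the time shift, in 1-minute steps on the watch log, that maximises the correlation with all of that subject's breath readings. State the search range in advance (the check here used −30 to 150 minutes).
- Report the mean, SD and 95% CI of the shift across subjects: on predicted BAL in Phase II, as residual lag, and on TAC in Phase I, as the characteristic lag of 4.2.2. This is a reporting measure and need not force the calibration model to be a pure delay.
- Keep the Tmax differences as a descriptive display, and treat the Tmax Pearson correlation in hypothesis 2 as descriptive as well.

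The cost is a few lines of text and code, with no new data, visits or subjects. The downside is that the shift assumes curves of broadly similar shape. If the watch broadens the signal, the shift and the peak difference are different quantities and both should be shown.
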